**University Hospitals Case Medical Center**  
**Department of Dermatology**  
**Protocol**

**Protocol Title:** Effects of UVB Excimer Laser on Serum Inflammatory Markers in Patients with Psoriasis

**Principal Investigator:** [name], NP

**Co-Principal Investigator:** [name]

**3.3.4 Visit 23: Final Visit/Early Termination Visit [2 days-2 weeks after last treatment]  
(estimated time: up to 1 hour )**

- Subjects will have their psoriasis clinically evaluated through PASI scoring and PGA.
- Treated plaques will be evaluated using a chromameter to measure hyperpigmentation and erythema that may be caused by the laser.
- Subjects may have plaque/body photographs taken.
- Subjects will undergo a post-treatment blood draw.
- Optional, post-treatment punch biopsies may be taken from a psoriasis lesion.
- Subjects will fill out the Patient Satisfaction Survey.

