## **1. BACKGROUND/RATIONALE**

Psoriasis is a prevalent global skin disease (1). Psoriasis is not simply an inflammatory disease of the skin but also a systemic inflammatory condition that carries a higher risk for cardiovascular disease and other systemic comorbidities. Certain inflammatory markers are known to be elevated in the serum of patients with psoriasis. Some of these markers may correlate with severity and extent of skin lesions (i.e. PASI score), while others may not (2). Therapies that decrease the inflammation present in the skin could lead to a systemic decrease in inflammatory mediators, thereby lowering the risk for developing comorbidities. UVB phototherapy has been employed in the treatment of psoriasis for decades. The UVB wavelengths most effective for psoriasis (i.e. action spectrum) falls within 308-313 nm. Narrowband UVB (311 nm) is the most popular phototherapeutic modality for full body treatment, in which unaffected normal skin is also exposed to UV light. Lesion targeted NUVB became feasible upon the introduction of 308 nm excimer lasers. This strategy not only spared normal skin from unnecessary UV, but also allowed for higher doses of UV to be delivered on lesional skin, within a reasonable amount of time. Currently, excimer laser treatment of psoriasis is an FDA-approved therapy. Whereas changes in serum resistin have been demonstrated after NUVB (3), there is no data regarding targeted UVB excimer laser treatments and serum inflammatory markers.

Hyperpigmentation is a common adverse effect reported after targeted UVB phototherapy (4,5). In our clinical experience, the Photomedex Xtrac® Velocity Excimer Laser has resulted in minimal to no hyperpigmentation after psoriasis plaque treatment. Furthermore, there is a lack of research objectively measuring hyperpigmentation and erythema after excimer laser treatment.

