## **2. STUDY OBJECTIVES/HYPOTHESIS**

The overall aims for this study are to determine whether UVB excimer laser treatment of psoriasis affects serum inflammatory markers, and to assess hyperpigmentation and erythema with excimer laser treatment.

We hypothesize that treatment of psoriasis with UVB delivered via 308 nm excimer laser will decrease the levels of serum inflammatory markers. We hypothesize that treatment will decrease plaque erythema and will result in minimal hyperpigmentation

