## **3. STUDY DESIGN**

We plan on enrolling 24-27 psoriasis patients for this research study.

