#### **3.2.2 Excimer Laser Irradiation:** This is a standard clinical procedure approved for the treatment of psoriasis. Initial laser dose will be anywhere from 1-4x the MED,

**University Hospitals Case Medical Center**  
**Department of Dermatology**  
**Protocol**

**Protocol Title:** Effects of UVB Excimer Laser on Serum Inflammatory Markers in Patients with Psoriasis

**Principal Investigator:** [name], NP

**Co-Principal Investigator:** [name]

depending on thickness of the plaque. Escalation will be 25-50% increase in dose per treatment if there is no residual erythema, 25% increase per treatment if there is mild residual erythema, and 0% increase per treatment if there is moderate residual erythema. Investigator also has the option to skip a treatment, if there is above moderate erythema, or significant patient discomfort exists. Patients will receive treatment twice a week until one of the following:

- PASI 75 Improvement
- Patient reaches a maximum of 20 treatments

**3.2.3 Optional Punch Biopsy:** Up to 8mm punch biopsies may be taken at the screening visit and final visit from a psoriasis lesion. The tissue samples will be used for histology and undergo standard H&E staining to evaluate the differences before and after Excimer laser treatment. Patients may still participate in this study if they choose to not donate punch biopsies. This procedure involves the removal of a small circle of skin (pencil eraser-sized) using a cookie cutter-like instrument. Lidocaine is used to numb the area to be removed before obtaining the biopsy and then 1-2 stitches are used per biopsy site to prevent bleeding, speed healing and improve the appearance. This procedure may last up to an hour depending on the number of biopsy sites. The stitches are then removed 7-14 days later.

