**3.2.4 PASI Scoring:** PASI will be determined for all subject at the Screening Visit, Visit 8, Visit 16, at Visit 23 Final/Termination Visit and, if applicable, the 3 month follow-up visit. The PASI is a measure of psoriatic disease severity taking into account qualitative lesion characteristics (erythema, thickness, and scaling) and degree of skin surface area involvement on defined anatomical regions. The PASI is a validated instrument that has become standard in clinical trials for psoriasis. Psoriasis Area Severity Index scores range from 0 to 72, with higher scores reflecting greater disease severity. Erythema, thickness, and scaling are scored on a scale of 0 (none) to 4 (very severe) on 4 anatomic regions of the body: head, trunk, upper limbs, and lower limbs. Degree of involvement on each of the 4 anatomic regions is scored on a scale of 0 (no involvement) to 6 (90% to 100% involvement). The total qualitative score (sum of erythema, thickness, and scaling scores) is multiplied by the degree of involvement for each anatomic region and then multiplied by a constant. These values for each anatomic region are summed to yield the PASI score.

**3.2.5 Physician Global Assessment (PGA):** PGA skin evaluation will be performed at the Screening visit, Visit 8, Visit 16, Visit 23 Final/Early Termination Visit, and, if applicable, the optional 3 month follow-up visit. This assessment is a scale from 0 (clear) to 5 (severe). It is a global assessment of the subject's psoriasis based on the severity of induration, scaling and erythema.

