#### **4. RISKS AND DISCOMFORTS AND HOW MINIMIZED**

- 4.1. Sunburn Test/Minimum Erythema Dose (MED) Testing:** A sunburn reaction may result from the MED testing. The degree of sunburn that the participant experiences should be light to moderate redness (sometimes no redness occurs). It may result in some tenderness and possibly some mild dryness and itching and may change into a tan color, with the degree of darkness and the time it takes to fade being dependent upon the light dose and participant skin type. In the most extreme circumstance, to achieve a completely even color of light-exposed and adjacent unexposed skin can take over one year, and in most cases, will result in no long-term effects from this type of exposure. Some sunburns will not be visible, so the area will be marked with a black pen to facilitate evaluation.
- 4.2. Excimer Laser Irradiation:** Similar to a sunburn, there could be redness, scaling, occasionally blistering of the skin lesion treated. These are considered expected reactions to the ultraviolet light. As this is a therapeutic, clinical intervention that is known to reduce the inflammation in psoriasis, the benefits outweigh the risks and discomforts. Long-term risks of UVB Excimer laser have not been reported in the literature.
- 4.3. Chromameter Assessment:** The chromameter poses minimal risk, as this is a non-invasive instrument that is used to measure pigmentation and redness.
- 4.4. Optional Punch Biopsies:** Punch biopsies will be up to 8mm in diameter. Lidocaine, which is used to numb the skin prior to biopsy, may cause a tingling or burning sensation when injected into the skin. Potential risks of the biopsy include bleeding or oozing from the biopsy wound, discomfort at the site, or infection. One to two sutures will be utilized to close the biopsy site. These will be removed 14 days after the biopsy occurs. Suture removal is generally painless, but may involve a scant amount of bleeding and some pinching or pulling of the skin. The biopsy site will heal with a small, flat scar, which may be red for several months. The scar may be lighter or darker than the surrounding area.
- 4.5. Blood Draw:** The risks of simple blood drawing may commonly include the occurrence of discomfort and/or bruise at the site of the puncture and, less commonly, the formation of a small clot, swelling of the vein, or bleeding from the puncture site.

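### Does a final visit 2 days to 2 weeks after the last laser dose undermine the reading of plaque erythema?

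*Combined protocol and SAP*

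**What the plan says.** - **Timing.** The heading of protocol section 3.3.4 reads "Visit 23: Final Visit/Early Termination Visit [2 days-2 weeks after last treatment". PASI, PGA, chromameter and the post-treatment blood draw are all procedures of that one visit.
- **Hypothesis.** Section 2 states: "We hypothesize that treatment will decrease plaque erythema and will result in minimal hyperpigmentation".
- **Measure.** Sections 3.2.6 and 14.4 assess erythema by a*, compared with untreated skin and between visits. Sections 3.3.3 to 3.3.5 give the chromameter a further purpose: to pick up erythema and hyperpigmentation caused by the laser.
- **Expected reaction.** Section 4.2 warns that "there could be redness, scaling, occasionally blistering of the skin lesion treated".
- **Dose rule.** Section 3.2.2 sets escalation by the redness still present: "25-50% increase in dose per treatment if there is no residual erythema, 25% increase per treatment if there is mild residual erythema", no increase for moderate redness, and an option to skip a session above that. On frequency it says: "Patients will receive treatment twice a week until one of the following".
- **PASI and PGA.** Both include erythema and scaling. For PASI, section 3.2.4 says: "The total qualitative score (sum of erythema, thickness, and scaling scores) is multiplied by the degree of involvement for each anatomic region". Section 14.1 summarises percent change in PASI descriptively.
- **Size.** Section 3 says: "We plan on enrolling 24-27 psoriasis patients for this research study". No test, SD, effect size or power target is given.

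**The concern.** The hypothesis is that plaques become less red, yet the treatment itself can redden them for a time. Treatment twice a week means an average gap of 3.5 days, and the dose rule allows for redness still visible at the next session. Visit 23 can come sooner than that, on day 2, or as late as day 14. Two patients with the same true response could therefore give different final a* values only because of when they were seen.

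Comparison with normal skin does not remove this. Section 1 says of lesion-targeted treatment: "This strategy not only spared normal skin from unnecessary UV". The reference skin therefore carries no laser redness to subtract. The 3-month visit is well clear of the acute phase but is optional. Section 14 has no term for days since the last dose.

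At stake is a fall in plaque erythema that is understated or missed, plus extra between-patient variation. In the comparison of screening with Visit 23 the bias would not manufacture a benefit, because screening precedes any laser treatment of the plaques. That protection does not extend to every visit-to-visit comparison: redness fading between Visit 16 and a late Visit 23 could look like improvement.

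**Working it through.** The plan states no figure on this point, so there is none to reproduce. The check has four parts.

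**1. Timing (sections 3.2.2, 3.3.3, 3.3.4).**
- Mean treatment gap: 7/2 = 3.5 days.
- Visit 23 in units of that gap: 2/3.5 = 0.57 to 14/3.5 = 4.0.
- Treatment visits run from 3 to 22, so Visit 8 is treatment 8 − 2 = 6 and Visit 16 is treatment 16 − 2 = 14 if none is skipped.

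Residual redness at Visit 23 is therefore possible. It is not certain, since absence of residual redness is the first category of the dose rule.

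**2. What moving the visit later would do.** Assume redness decays exponentially from its day-2 level with half-life *h*, and visits are spread uniformly. The mean fraction left over days *a* to *b* is [e^(−k(a−2)) − e^(−k(b−2))] / [k(b − a)], with k = ln 2 / h. The half-lives are assumptions.

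| h (days) | Visits on days 2-14 | Visits on days 8-14 |
|---|---|---|
| 1 | 0.120 | 0.004 |
| 3.5 | 0.382 | 0.178 |
| 7 | 0.585 | 0.416 |

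Whatever is removed as contamination of the plaque-erythema comparison is also removed as signal from the laser-erythema reading, because both use the same a* value.

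**3. What an analysis by days since last dose could show.** Regress final a* on days since the last dose. The 95% half-width for the day-2 versus day-14 difference, in residual SDs, is t(0.975, n−2) × 12 / √SSx, where SSx is the sum of squared deviations of the visit days. With evenly spaced visits:

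| n | Days | SSx | t | Half-width |
|---|---|---|---|---|
| 24 | 2-14 | 313.0 | 2.074 | 1.41 |
| 27 | 2-14 | 348.9 | 2.060 | 1.32 |
| 24 | 8-14 | 78.3 | 2.074 | 2.81 |
| 27 | 8-14 | 87.2 | 2.060 | 2.65 |

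A difference across the window would have to exceed about 1.3 SD before its interval excluded zero. Scheduling visits late doubles that figure, so the two obvious remedies work against each other.

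**4. Power of the screening versus Visit 23 comparison.** Assume a paired t-test, two-sided 5%, noncentral t. The true fall and the leftover redness, both in SDs of change, are assumptions. Ranges cover n = 24 and n = 27.

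| True fall | Leftover 0 | 0.1 | 0.2 | 0.3 |
|---|---|---|---|---|
| 0.60 (n=24) or 0.56 (n=27) | 80% | 63-65% | 44-46% | 26-29% |
| 0.8 | 96-98% | 91-94% | 80-85% | 65-71% |
| 1.0 | above 99% | 99% | 96-98% | 91-94% |

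The first row looks alarming only because it starts at exactly 80%, where power is most sensitive to a shift. With a true fall of 1.0 SD the same contamination leaves at least 91%. The documents do not say which row applies.

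**The case for a change.** The best case for a change is that it would be cheap. Visit dates already give the interval since the last dose. A few sentences could name the comparison that tests the hypothesis, require readings before the laser at Visits 8 and 16, and ask for Visit 23 late in its window. A reader could then tell absence of benefit from leftover redness.

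Part of this stands. The same a* value serves two aims, and nothing in section 14.4 separates them. But each proposed remedy fails to earn its place:

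- **Later scheduling** weakens the measurement of laser-caused erythema and would make the laser look milder. Visit 23 is also a single visit: moving PASI and a* either moves the blood draw with them or needs a second visit. Splitting them would separate final PASI from the serum sample that section 14.2 correlates with it.
- **Days since last dose** as an analysis is too imprecise to alter a conclusion.
- **Order at Visits 8 and 16** is already implied. Section 3.3.3 lists the readings before the laser, and the dose rule needs redness judged before dosing.
- **Naming the comparison** is detail that analysts supply naturally. Screening against the final visit is the obvious reading of a hypothesis about the effect of treatment.
- **The 3-month a*** already falls under the visit-to-visit comparison in section 14.4.

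PASI and PGA add little to the case. The plan designates a* alone as its erythema measure. PASI is a composite summarised descriptively, section 14 specifies no PGA analysis, and nothing says that raters would score laser redness as psoriasis.

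**Conclusion.** The observation is sound, but it does not call for a change. Final a* may include laser redness in some patients, and this would tend to understate any fall from screening to Visit 23. The amount is unknown: power could fall from 80% to 26-29% or stay at 91% or more, depending on an assumed true effect and assumed contamination of up to 0.3 SD.

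The window is a fair trade-off, because one reading serves both the hypothesised fall in plaque redness and the record of laser-induced redness. Moving the reading favours one aim at the other's cost. Modelling the timing would give an interval of about ±1.3 to ±1.4 SD at best. The dose rule, which withholds escalation at moderate redness, gives some limit on severe carry-over, and the optional 3-month reading offers a partial check in those who attend.

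What remains is interpretation that competent analysts can supply: show days since last treatment beside the final a*, and acknowledge that the two sources of redness cannot be separated at that visit. The conclusion would differ if the documents showed that laser redness is large and long-lasting relative to the expected fall in a*; they give no such figures.

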**3.3.5 \*\*Optional 3 Month Follow-Up Visit (estimated time: approximately 30 minutes):**

- Subjects will have their psoriasis clinically evaluated through PASI scoring and PGA.
- Treated plaques will be evaluated using a chromameter to measure hyperpigmentation and erythema that may be caused by the laser.
- Subjects may have plaque/body photographs taken.

**3.4 Schedule of Events**

	Visit 1: Screening	Visit 2 (Only if Sunburn/MED was done)	All Treatment Visits (Visits 3-22)	Treatment Visit 8 and Visit 16	Visit 23: Final Visit/Early Termination Visit	**Optional 3 Month Follow- Up Visit
Informed Consent	X					
Limited Medical Exam	X					
PASI & PGA	X			X	X	X
Photographs*	X	X	X	X	X	X
Chromameter	X			X	X	X
Blood Draw	X				X	
Concomitant Med Assessment	X	X	X	X	X	X
Optional Sunburn/MED Test	X					
Optional Sunburn/MED assessment		X				
Excimer Laser Treatment			X	X		
Nutrition Questionnaire	X					
Patient Satisfaction Questionnaire					X	
Adverse Event Assessment	X	X	X	X	X	X
Optional Sub-Study: Additional Blood	X				X	
Optional Sub-Study: Punch Biopsy	X				X	

*\*Photographs will be taken throughout this study at the discretion of the study doctor to document any changes in the psoriasis from the laser treatment.*

#### **4. RISKS AND DISCOMFORTS AND HOW MINIMIZED**

- 4.1. Sunburn Test/Minimum Erythema Dose (MED) Testing:** A sunburn reaction may result from the MED testing. The degree of sunburn that the participant experiences should be light to moderate redness (sometimes no redness occurs). It may result in some tenderness and possibly some mild dryness and itching and may change into a tan color, with the degree of darkness and the time it takes to fade being dependent upon the light dose and participant skin type. In the most extreme circumstance, to achieve a completely even color of light-exposed and adjacent unexposed skin can take over one year, and in most cases, will result in no long-term effects from this type of exposure. Some sunburns will not be visible, so the area will be marked with a black pen to facilitate evaluation.
- 4.2. Excimer Laser Irradiation:** Similar to a sunburn, there could be redness, scaling, occasionally blistering of the skin lesion treated. These are considered expected reactions to the ultraviolet light. As this is a therapeutic, clinical intervention that is known to reduce the inflammation in psoriasis, the benefits outweigh the risks and discomforts. Long-term risks of UVB Excimer laser have not been reported in the literature.
- 4.3. Chromameter Assessment:** The chromameter poses minimal risk, as this is a non-invasive instrument that is used to measure pigmentation and redness.
- 4.4. Optional Punch Biopsies:** Punch biopsies will be up to 8mm in diameter. Lidocaine, which is used to numb the skin prior to biopsy, may cause a tingling or burning sensation when injected into the skin. Potential risks of the biopsy include bleeding or oozing from the biopsy wound, discomfort at the site, or infection. One to two sutures will be utilized to close the biopsy site. These will be removed 14 days after the biopsy occurs. Suture removal is generally painless, but may involve a scant amount of bleeding and some pinching or pulling of the skin. The biopsy site will heal with a small, flat scar, which may be red for several months. The scar may be lighter or darker than the surrounding area.
- 4.5. Blood Draw:** The risks of simple blood drawing may commonly include the occurrence of discomfort and/or bruise at the site of the puncture and, less commonly, the formation of a small clot, swelling of the vein, or bleeding from the puncture site.
- 4.6. Questionnaires:** There are no known risks to filling out questionnaires. However, in rare instances some participants may feel uncomfortable with answering or applying responses to some questions.
- 4.7. Photographs:** There are no known risks to taking photographs. In the event a photograph is taken of the face or any other identifiable feature, the patient's identity may be known. Every precaution will be taken to protect the patient's identity. In the event a photograph is taken of

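### Section 4.2 omits pigment change from the laser's expected reactions, and section 14.4 plans no count of patients whose treated skin darkens

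*Combined protocol and SAP*

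**What the plan says.** Section 4.2 (Excimer Laser Irradiation) states: "Similar to a sunburn, there could be redness, scaling, occasionally blistering of the skin lesion treated". It describes these as expected and does not mention pigment. It adds: "Long-term risks of UVB Excimer laser have not been reported in the literature".

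Section 1 states: "Hyperpigmentation is a common adverse effect reported after targeted UVB phototherapy (4,5". It places the study laser in that class: "Lesion targeted NUVB became feasible upon the introduction of 308 nm excimer lasers". It also reports that, in the site's own clinical experience, the named device "has resulted in minimal to no hyperpigmentation after psoriasis plaque treatment".

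Section 2 makes hyperpigmentation a study aim and hypothesises that it will be minimal. Sections 3.3.3, 3.3.4 and 3.3.5 have treated plaques measured by chromameter for hyperpigmentation that the laser may cause.

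Section 4.1, on the MED test, says the exposed spots may tan. It continues: "In the most extreme circumstance, to achieve a completely even color of light-exposed and adjacent unexposed skin can take over one year". The same sentence goes on to say that lasting effects are not expected for most people.

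Section 14.4 assesses hyperpigmentation through L\*. Treated plaques are compared with untreated skin and from visit to visit, and the values are correlated with response to treatment.

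**The concern.** A risk section should list the reactions that the rest of the protocol treats as likely. Here the reaction left out of 4.2 is one that the study sets out to measure. The sentence on long-term risks then follows a list with no pigment change in it, and nothing points the reader to the colour-change caution one item earlier.

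Two things are at stake. The first is the accuracy of the risk statement, and of any consent text drawn from it. The second is the evidence for the hypothesis of minimal hyperpigmentation. A reader will want to know how many patients visibly darkened, and the analysis plan does not produce that number.

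**Working it through.** The first part is a comparison of texts. The plan states no figure to reproduce.

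**1. Does the class statement in section 1 cover the study laser?** Yes. Section 1 attributes hyperpigmentation to targeted UVB phototherapy and names the 308 nm excimer laser as the device that made lesion-targeted treatment feasible. The site's favourable experience lowers what one might expect from this device. It is uncontrolled, however, and it is the proposition that section 2 puts to the test.

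**2. How does section 4 treat colour change elsewhere?**

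| Procedure | Section | Colour change disclosed? |
|---|---|---|
| MED test | 4.1 | Yes: tanning, over a year to even out in the extreme case |
| Excimer laser treatment | 4.2 | No |
| Optional punch biopsy | 4.4 | Yes: scar may be lighter or darker |

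**3. Is there a reason in the documents for 4.1 to mention pigment and 4.2 not to?** None was found. Section 3.2.1 says the MED test is done with the excimer laser, so the light source is the same. Section 4.1 says that darkness and fading time depend on light dose and skin type. Under sections 3.2.1 and 3.2.2, treatment starts at 1 to 4 times the MED and may be given up to 20 times. Section 3.1.1 admits skin types I to VI. This reasoning supports mentioning pigment change in 4.2. It does not give a duration for treated plaques, because 4.1 concerns test spots on the buttock or lower back.

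**4. What will the analysis yield?** Section 14.4 sets no L\* threshold that would define hyperpigmentation in a patient, and it plans no incidence. Section 3.4 schedules adverse event assessment at every visit, so darkening can be recorded. No section asks for it by name, and grade 0 in section 15.1 includes findings judged not clinically significant. Cosmetic darkening could therefore be recorded unevenly.

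**5. What would a count show at this sample size?** Section 3 plans 24 to 27 patients. For zero affected out of n, the upper limit p of the exact two-sided 95% interval solves (1 − p)^n = 0.025, so p = 1 − 0.025^(1/n).
- n = 24: 1 − 0.025^(1/24) = 0.1425, reported as 14.2% (unrounded 0.14247).
- n = 27: 1 − 0.025^(1/27) = 0.1277, or 12.8%.

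These limits show the precision of the proposed summary in its most favourable outcome. They do not measure the omission in 4.2.

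**The case against.** The case for leaving the plan alone has real content.

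- **Section 4.2 is silent on pigment; it does not deny it.** This stands. A reader might infer that the protocol contradicts itself. But section 1 says common, not long-lasting, and 4.2 speaks only of what the literature has reported on long-term risk. The two can both be true, so the fault is an omission.
- **The one-year figure is an extreme case for test spots.** This stands. A reader might infer that treated plaques can stay dark for over a year. No section gives a duration for them, and 4.1 adds that most cases have no long-term effects.
- **Staff are told about hyperpigmentation elsewhere.** This stands. It appears in section 2, 3.2.6, 3.3.3 to 3.3.5 and 14.4, so one cannot conclude from section 4 that staff go unwarned. Nor can one say that participants do, since the consent pages were not available for review.
- **Adverse events are checked at every visit, and section 15 names no specific reaction.** This stands. Darkening is already recordable, and its absence by name from section 15 is not a defect peculiar to it.
- **Section 14.4 does not specify group means.** This stands. A reader might assume a comparison of mean L\*, but the text says only that values are compared and correlated. The gap is the missing per-patient count, whatever summary of L\* is used.
- **The protocol deliberately chose an objective measure.** This stands in part. A visual item is subjective and, in this study, unblinded. That is a reason to keep the chromameter as the main measure, but a yes/no count beside it answers a question that L\* without a threshold does not.

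**Conclusion.** The concern holds in a limited form. Section 4.2 omits a reaction that section 1 calls common for this class of treatment and that the visit schedule measures as a possible laser effect, while 4.1 and 4.4 disclose colour change for lesser procedures. Separately, the hypothesis of minimal hyperpigmentation has no planned incidence behind it.

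The omission has no numerical size. The 14.2% and 12.8% limits assume that all 24 or 27 planned patients are assessed and that none darkens. They should not be read as an estimate of risk or as the cost of the omission.

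The conclusion rests on the protocol text alone. Whether the literature reports long-term risks of the excimer laser cannot be judged from these documents, so there is no basis for calling that sentence wrong. It needs a cross-reference and need not be deleted. The study remains workable as designed.

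**What to change.** 1. In 4.2, add hyperpigmentation of treated skin to the expected reactions. Qualify the long-term sentence by referring to the colour-change caution in 4.1, without stating a duration for treated plaques.
2. Check that the consent text matches, and amend it only if it does not.
3. At the adverse event checks already marked in section 3.4, add one yes/no item: visible darkening of treated sites. The visit lists in 3.3.4 and 3.3.5 do not repeat the adverse event check, so name the item there too.
4. In 14.4, report the proportion of patients affected with an exact 95% interval beside the L\* results, and state that the visual item supplements the chromameter and does not replace it.

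The cost is a few lines in 4.2, 14.4 and the visit lists, one item on an existing form, and possibly a consent edit. No visits, equipment or patients are added. The one drawback is the subjectivity of an unblinded visual rating, which should be acknowledged when the proportion is reported.
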